### 1. Introduction/Background

More than half of all colon cancer is diagnosed at a stage of regional or distant metastasis. The standard treatment for these late stage malignancies includes surgery and adjuvant chemotherapy with a combination of drugs including platinum-based therapy (e.g FOLFOX). These treatments, while demonstrating improvement in survival, often have severe side effects that can be both transient and long-lasting. Although the microbiome field of research is still relatively nascent, mounting evidence indicates that the gut microbiome influences the development and treatment of colon cancer through several factors including modulation of the immune system. Specifically, *F. nucleatum* colonization in murine models of colon cancer (*Apc*Min/+) increases tumor multiplicity by various mechanisms including favoring the infiltration of tumor-promoting myeloid cells to create a pro-inflammatory environment. However, the microbiome field still lacks critical *prospective* studies to determine causation, which is the focus of this proposal.

Recently, multiple murine studies demonstrated that treatment efficacy depends in part on the microbiome-immune system interactions. Specifically, destruction of the microbiome through use of antibiotics resulted in a compromised efficacy of immune stimulating and platinum-based chemotherapeutics. In addition, commensal bacteria can enhance treatment through increased secretion of TNF- $\alpha$  in tumor-associated myeloid cells. Supporting this evidence in patients with melanoma, investigators were able to use the initial microbial community structure (shot-gun DNA sequencing) to identify bacterial pathways (polyamine synthesis, B vitamin metabolism) that were able correctly predict colitis development after treatment with the immunotherapeutic agent ipilimumab (anti-CTLA-4) (Dubin, 2016). Several fundamental questions therefore remain unanswered 1) how do prophylactic antibiotics prior to treatment change the microbiome and its function in relationship to with treatment outcome? 2) does the microbial community structure prior to treatment influence or predict treatment outcome, survival or recurrence in colorectal cancer (CRC) patients? 3) how does the microbiome-immune system relationship change during anti-cancer therapy? We propose to address these last two questions in a prospective incident cohort of colorectal cancer using patients recruited from the Baylor Scott and White Healthcare System. This study will collect multiple biospecimens (stool, blood, tissue) before, during and after treatment. These data will enable us to measure the microbiome-immune system relationship at multiple time points to determine the effect on side-effect type and severity, and on colon cancer recurrence (stage II/III) and survival. The results from this study will 1) assist patients and clinicians in making informed treatment decisions, and 2) potentially lead to new therapeutics to increase survival, reduce treatment side effects and prevent recurrence of colon cancer.

### 2. Significance

Why is the microbiome important in colon cancer treatment and outcome? Overall, colorectal cancer (CRC) accounts for approximately 142,000 new cancer cases and 50,000 cancer deaths annually, making it the second most lethal cancer in the U.S. (SEER). Alarmingly, a recent report indicates that CRC is on the rise among those younger than 55. Unfortunately, more than half of all colon cancer is diagnosed at a stage of regional or distant metastasis. The standard treatment for these late stage malignancies includes surgery and adjuvant chemotherapy with a combination of drugs including antibiotics and platinum-based therapy. One of the methods that has shown promise for identifying early stage colon cancer, response to treatment is the microbiome of the gastrointestinal tract (GI). The quantity of microorganisms present in the human gastrointestinal (GI) tract are approximately equal to the number of human cells, yet their collective genomes, the microbiome, exceeds our own genome by over 100-fold. Therefore, the

potential of the microbiome to affect cancer etiology, inflammation, treatment and survival is substantial. Several lines of evidence already support this idea, demonstrating an intimate relationship between the microbiome, its structure, and metabolic products and the immune system. However, these studies have only been conducted in animal models of cancer. While case-control studies in humans have demonstrated an association between the microbiome and immune system in individuals with cancer, we lack an understanding of the causal effects; how the microbiome affects the immune system response and colon cancer treatment, recurrence or survival. This gap in understanding of causation can thus only be addressed in a prospective study of colon cancer, which is a specific directive from the Whitehouse Microbiome Initiative.

By prospectively characterizing the colon cancer microbiome and immune system responses, we can address multiple outstanding questions. First, does an individual's core or initial microbiome/community structure predict treatment response, recurrence or survival? Second, how much of an effect does the microbiome have on the immune response during and after cancer treatment, and how long does it take the microbiome to recover (if it does)? Does, does gut barrier integrity or biofilm formation predict treatment outcome?

Answers to these important question, can be used to not only enrich our understanding of the mechanisms important to the microbiome-immune system relationship, but will directly inform future decision in colon cancer treatment. Most important, these results may uncover potential therapeutics for cancer treatment and side-affect mitigation, such as chemotherapy-induced diarrhea, which affects over 50% of patients undergoing anti-cancer therapy for CRC. For example, it may be prudent to first restructure the microbiome to establish a more conducive environment prior to treatment to enable the most effective treatment response. Further, it may be possible to leverage the immune system by engineering probiotics that deliver anti-inflammatory cytokines that ameliorate inflammation after treatment. **Conducting this study is a significant part of the key steps in elucidating causal mechanisms underlying the impact of the microbiome-immune system relationship on efficacy of anti-cancer therapy, and determining the impact of diet and metabolite fluctuations in predicting recurrence and survival.**

### 3. Objectives & Specific Aims

**Objective:** This is a formative study to lay the groundwork for establishing a large cohort of incident colon cancer to examine the microbiome-immune relationship in colon cancer outcome. Our hypothesis is that colon cancer treatment, recurrence and survival are compromised by treatment-induced dysbiosis and dependent upon pre-treatment microbial structure. We plan to address this hypothesis with the following aims:

**Aim 1: Determine if the gut microbiome and microbial metabolites are altered in response to cancer treatment and correlate with CID incidence and severity in stage II/III colon cancer**

Sub-Aim1a: Quantify the gut microbiota prior to surgery and treatment, and at 3 time points during FOLFOX, and correlate with CID incidence and severity

Sub-Aim1b: Quantify microbial pathway abundance and fecal metabolite levels prior to, and during treatment, and determine their associations with incidence and severity of CID

Sub-Aim1c: Quantify circulating and tumor tissue cytokine levels prior to, and during treatment, and determine their associations with the gut microbiota, and incidence and severity of CID

**Aim 2: Determine if the dietary history or dietar intake during treatment is associated with CID incidence and severity in stage II/III colon cancer**

Primary outcomes: CID incidence and severity and gut microbiome and metabolome changes. The patients with colon cancer, serving as their own controls, will provide stool samples that enable clinicians to predict toxicity of anti-cancer therapy in stage II/III colon cancer patients.

Secondary outcomes: Circulating cytokines, dietary history and changes during treatment, stool index changes

## 4. Methodology

### 4.1 Study Design.

While incident colon cancer studies have been conducted, none have integrated the analysis of the microbiome with other clinically relevant factors. With the recent evidence from animal models demonstrating the importance of the microbiome-immune relationship in shaping the efficacy of anti-cancer treatment, a prospective human study is critical to understand how and if these results translate to human colon cancer. In general, however, there is a paucity of prospective human microbiome studies addressing the microbiome-host relationship. Thus, this study design will address several outstanding issues in the fields of cancer and microbial ecology.

In order to understand the causative factors in response to colon cancer treatment and identify predictive biomarkers, and prospective cohort study is necessary. As previously discussed, the outstanding questions that will be answered through this type of study design are 1) whether the initial microbiome/community structure predicts treatment toxicity, and 2) the impact of the diet and microbiome on the immune response during and after cancer treatment, and its resiliency after cessation of treatment. By collecting multiple types of specimens before, during and after treatment with extensive follow up, we will be able to answer the first questions regarding predictive biomarkers that individually or in combination predict response to treatment. We will also be able to use these data to identify mechanisms in the causal pathway of response to treatment that can be used in future studies to improve survival or reduce recurrence.

This will be a large prospective cohort of incident colon cancer. For this protocol, there is no group assignment, randomization or placebo group. Study Day 0 for this protocol will be considered when the patient is diagnosed with colon cancer after consent, and separately Treatment Day 1 is the day on which the patient starts their first chemotherapy infusion (lasting 12 weeks). All stool samples collected will be considered beyond standard of care (SOC), however, all blood samples will be taken as part of SOC, with the exception that an 2 additional vials of blood will be taken for immune marker analysis. Briefly, samples for this project will include:

- A. After pre-study consent, the day prior to colonoscopy for colon cancer screening/detection, a stool (patient-collected) sample will be collected prior to bowel prep for colonoscopy. If, for some reason, this is not possible to do by the patient, then the physician will collect a rectal swab during colonoscopy (**Visit 1**). One stool sample (self-collected) the day prior to the first outpatient appointment before start of treatment (between Days 21-28) – Pre-Treatment (**Visit 2**) 3. Once IV chemotherapy begins, this will be designated at treatment day 1 (TD1). After the IV chemo rounds 2 (**Visit 3, treatment day 15**), 6 (**Visit 4, treatment day 71**) and 10 (**Visit 5, treatment day 128**), stool will be collected by the patient at home the day before starting chemo and on the 2nd day (or within 72 hours to account for constipation/diarrhea) after the last treatment day of that round of IV chemo for that session. Specifically, one stool will be collected on TD 15 and 19 (or the day before the next IV chemo round starts) after the 2nd round of IV chemo; on TD, 71 and 75 (or the day before the next IV chemo round starts) after the 6th round of IV chemo; and on TD 128 and 131 (or the day before the next round of IV chemo) after 10th round of IV chemo treatment. Blood draw is SOC, however, stool samples will be requested in addition to SOC.
- B. A blood sample taken at the same time as blood is draw for standard clinical treatment when the patient goes in for the clinical visit or treatment by the REA during usual blood draw times (Surgery Day and on the outpatient visit prior to treatment; Treatment Days 15, 71, 128).
- C. Tissue samples from the patient's resected tumor and non-tumor adjacent tissue after resection surgery will be collected for 1) fresh/frozen and 2) Carnoy's fixitive. Specifically, the physician will take a larger piece of both tumor and non-tumor adjacent tissue so that a small piece of each can be stored for analysis. After specimen collection and ID coding, microbial DNA will be isolated from the microbiome specimens and fecal and circulating metabolites identified. The DNA will be used to conduct microbial DNA sequencing (metagenomics) in accordance with existing protocols through the Integrated Human Microbiome Project (iHMP) study of IBD. The fecal metabolites will be used

to produce spectral profiles for quantification using protocols from the iHMP; performed at Baylor University in the laboratory of [name]. RNA will be isolated from tissue samples and separate section preserved in Carnoy's to determine biofilm formation and specific bacterial species present. RNA will be used to conduct gene expression assays (cytokines), and blood samples will be used to conduct serum cytokine assays and blood metabolite analysis.

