**The third through fifth study visits** (1 hour each) will take place on the 2nd(TD 15), 6th (TD 71) and 10th (TD 128) rounds of IV chemo of treatment (i.e. chemotherapy) at the BSWH center at which they are having their treatment. During this study visit, 2 blood vial samples will be taken as part of the routine clinical visit and the patient will be given two additional stool sample kits to take home to collect stool on the day before chemo starts and before chemo begins and the 2nd day and after their chemotherapy round is complete (i.e. if the infusion starts on Monday, the subject collect a stool sample on that Friday). After

each study visit, the patient will produce 2 stool samples (day before chemo starts and on the 2nd day after their chemo round ends) and drop it off at their treatment hospital or mail (FedEx) it into to the sequencing center at Baylor University. Again, they will be asked to complete the online 24 hour dietary recall (**ASA24**) at home within 72 hours of producing the stool samples. This is the same procedure that will be followed in the fourth and fifth study visits. During each of these visits, the REA or GI physician will ask about incidence and severity of chemotherapy induced diarrhea (**CTCAE – Gastrointestinal/Diarrhea, Grade 1-5**).

The REA will either call the subject or send a text message (if subject agrees) through Twillo after each visit to remind the subject of the days that stool collection and 24 hour (ASA24) recalls should occur.

The REA will obtain interval information from the participant according to the protocol and will provide subjects with stipends for each stool collection provided, which will include \$20 for each specimen collected (stool) up to \$160. If the patient was unable to provide a stool sample at the designated time point due to treatment side-effects they will still be given the compensation for completing the study. Thus, if patients complete all sample collections and all follow up visits, they may receive up to \$160.

Only [name] and the REA will have access to the data-collection sheets and registration forms that will be kept in a locked cabinet at the clinical site.

**Primary data endpoint:** At the end of the observational study we will assess incidence, duration and severity of chemotherapy-induced diarrhea.

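### The protocol gives incompatible days for the on-treatment stools, so stools from different points in the chemotherapy cycle can be analysed as one time point

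*Protocol*

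**What the plan says.** Three parts of the protocol describe the on-treatment stools.

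- **Section 4.1, item A, general rule.** For rounds 2, 6 and 10, "stool will be collected by the patient at home the day before starting chemo". A second stool follows on the second day, "or within 72 hours to account for constipation/diarrhea) after the last treatment day of that round".
- **Section 4.1, item A, specific days.** For round 2, "one stool will be collected on TD 15 and 19 (or the day before the next IV chemo round starts". Round 6 has TD71 and TD75 with the same alternative. For round 10 the stools fall "on TD 128 and 131 (or the day before the next round of IV chemo".
- **Section 4.3, Study procedures.** Visits three to five "will take place on the 2 nd (TD 15), 6 th (TD 71) and 10 th (TD 128) rounds of IV chemo". Two stool kits are handed over at that visit, and after it "the patient will produce 2 stool samples (day before chemo starts and on the" second day after the round ends. The timing example is "if the infusion starts on Monday, the subject collect a stool sample on that Friday". The text also says that the first stool precedes chemotherapy.
- **Data Collection, Stool microbiome.** Here there is one on-treatment stool per round, on the second day after TD15, TD71 and TD128, and no pre-round stool.

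The day count starts from this definition: "Treatment Day 1 is the day on which the patient starts their first chemotherapy infusion (lasting 12 weeks". Section 4.4 compares treatment time points with baseline and relates microbiome and metabolite measures to chemotherapy-induced diarrhea (CID). It does not say which stool of a pair is used.

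**The concern.** The stool sample is the main exposure measurement of the study, and patients collect it at home across two sites. If the rules allow different days, one patient's round-2 stool may come from before the infusion, another's from a few days after it, and a third's from just before round 3. All three could carry the same time-point label.

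A treatment-versus-baseline difference, or an association with CID, would then average over cycle positions in proportions that nobody chose. A separate analysis plan could say which stool to use. It could not recover a stool taken on the wrong day.

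**Working it through.** **Inputs.** TD1 is the first infusion (section 4.1). Rounds 2, 6 and 10 are placed on TD15, TD71 and TD128 (sections 4.1 and 4.3). The Monday-to-Friday example (section 4.3) puts the post-round stool at start + 4 days.

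**Spacing.** I found no stated cycle length, so it is inferred: 15 − 1 = 14 days from round 1 to round 2, and (71 − 15)/4 = 14 days from round 2 to round 6. From round 6 to round 10 the stated days give (128 − 71)/4 = 14.25, which is not a whole number. Spacings of 13 days (TD14, 66, 118) or 15 days (TD16, 76, 136) fit none of the stated round days.

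**Formulas.**
- Start of round k = 1 + 14(k − 1).
- Day before the round = start − 1.
- Post-round stool = start + 4. It is the second day after the last treatment day, so the round ends at start + 2 and 72 hours later is about start + 5.
- Day before the next round = start + 13.

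| Round | Computed start | Day before | Stated first stool | Stated second stool | Start + 4 | 72-hour limit | Day before next round | Second day after stated visit day |
|---|---|---|---|---|---|---|---|---|
| 2 | 15 | 14 | 15 | 19 | 19 | 20 | 28 | 17 |
| 6 | 71 | 70 | 71 | 75 | 75 | 76 | 84 | 73 |
| 10 | 127 | 126 | 128 | 131 | 131 | 132 | 140 | 130 |

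Five of the six stated days reproduce (15, 19, 71, 75, 131). TD128 does not.

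**First stool.** The day-before rule gives TD14, 70 and 126. The stated days are TD15, 71 and 128: on the computed start for rounds 2 and 6, and one day after it for round 10. The round-10 pair is also only 131 − 128 = 3 days apart, against 4 for the other two. A kit handed over at the TD15 visit cannot be used on TD14. A day-before-chemotherapy stool produced after that visit can only precede a later round.

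**Second stool.** TD28 − TD19 = 9 days, and TD28 − TD20 = 8 days past the 72-hour limit. The gap from the stated second stool is the same for rounds 6 (84 − 75) and 10 (140 − 131). Position start + 13 is the next round's start − 1, so a TD28 stool counts as post-round 2 under one rule and pre-round 3 under the other.

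**Third schedule.** The Data Collection text gives TD17, 73 and 130, which match neither stool of any pair.

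**Stool counts.** Item A implies 2 + 3 × 2 = 8 stools per person, or 112 × 8 = 896. This agrees with the stipend ($160/$20 = 8). Data Collection implies 2 + 3 = 5, which agrees with the sample-size text (560/112 = 5). The protocol therefore carries two sampling plans.

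**Other labels.** Section 4.4 names weeks 4, 14 and 24. Counted from TD1 these are TD22–28, 92–98 and 162–168, which contain none of the stated stool days; the origin of those weeks is not given. A 12-week duration (84 days) also ends before TD128.

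**Illustration with assumed inputs only.** Let a share q of post-round stools fall on the late day, and let a fraction r of the acute change remain by then. The mean change at that time point becomes 1 − q(1 − r) of its acute value. For q = 10%, 25% and 50% this is 90%, 75% and 50% if r = 0; 95%, 87.5% and 75% if r = 0.5; and unchanged if r = 1. The protocol gives neither q nor r.

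**The case against.** Several counter-arguments have force.

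- **No within-round contrast is planned.** A reader might infer that a before/after-chemotherapy comparison within each round is compromised. Section 4.4 defines none. Paired collection suggests one, but the stated comparisons are with baseline and with CID. This stands, so the point rests on those analyses.
- **Selective late collection is not documented.** A reader might infer that patients with bowel symptoms take the late option, which would tie timing to the outcome. The allowance for constipation and diarrhea is attached to the 72-hour window, not to the later day, and nothing says who uses the later day. Section 4.3 foresees that some patients cannot provide a stool because of side effects. This stands.
- **Recovery by day 13 is not documented.** Section 2 asks how long the microbiome takes to recover, if it does. A TD28 stool is at a different cycle position, but it cannot be called recovered.
- **The late option is one named day.** The text does not allow any day up to the next round.
- **The first-stool conflict is softer for rounds 2 and 6.** Section 4.3 repeats the day-before rule and says the stool precedes chemotherapy, so TD15 may be shorthand for the visit. That leaves the kit hand-out and TD128 unexplained.
- **The alternative may be misplaced.** It could be a garbled reference to the pre-round stool, given that both kits are handed out at the visit. This reading is possible. It would remove the late fallback, but the first stool would then belong to the next round.
- **Dates may already be recorded.** A stool collection form exists, though its content is not shown. Date labelling of clinical specimens is mentioned under the cytokine heading.

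**Conclusion.** The contradiction is real and lies in the current text. Sections 4.1 and 4.3 and the Data Collection section cannot all be followed. The main gap is in the post-round stool: a 72-hour window beside an alternative 9 days after the stated day, at the next round's pre-infusion position. The pre-round stool is a day or two out on paper (TD14/70/126 against TD15/71/128), and its kit arrives too late for the first of these days. Whether a pre-round stool is collected at all differs between sections.

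These figures assume the inferred 14-day spacing and the Monday-to-Friday example. The consequence is that unlike stools can share a time point in the treatment-versus-baseline and CID analyses. The documents do not establish the direction or size of any bias, or a link between late collection and symptoms. This should be corrected, because it determines what is sampled and is cheap to settle.

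**What to change.** Reconcile section 4.1 item A, section 4.3 Study procedures and the Data Collection text to one sampling schedule, starting with whether each round has one stool or two. If two are kept:

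1. Define the pre-round stool as the last stool before the actual start of that infusion, and supply its kit at the preceding contact.
2. Define the post-round stool as within 72 hours of the end of the round.
3. Delete the day-before-next-round alternative, or code such stools as a separate sample type outside the post-round time point.
4. Record the actual date and time of every stool.
5. State which stool of each pair enters each section 4.4 analysis, and align the planned stool total with the schedule.
6. Reconcile the treatment-day labels, TD128 included, with the actual round dates. This implies no view on the treatment schedule itself.

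The cost is more than wording: kits must go out earlier, and some late stools will leave the post-round time point.
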